## 9.7.3 Summary of HCP Characteristics

The following demographic information of participants will be summarized using the Completed Surveys analysis set:

- Number and percent of HCPs by age groups.
- Number and percent of HCPs by number of patients counseled regarding Casgevy as a treatment option.
- Number and percent of HCPs by profession.

# 9.7.4 Analysis for Objective of HCPs' Understanding of the Important Safety Information in the Guide for HCPs

Eighteen knowledge questions will test the HCPs understanding of 4 KRMs. The response to each of the 18 questions will be categorized as correct or incorrect. The table below outlines the 4 KRMs and the individual questions evaluating each message.

Using the Completed Surveys analysis set, the rate of correctness (percentage of correct answers) will be summarized for each of the 4 KRMs. The aRMM pertaining to each KRM will be considered successful if the correct rate for the specific KRM is at least 80%.

In addition, the source of knowledge of the safety information will also be summarized. KRM	Desired Response
Please indicate if each provided statement is correct or incorrect.	
KRM 1 Delayed Platelet Engraftment	
8. Casgevy has not been associated with delayed platelet engraftment.	9 and 12 marked as
9. Patients receiving Casgevy should be counseled on signs and symptoms of bleeding.	correct.
10. If a patient experiences petechiae prior to achieving platelet engraftment, there is no need to perform a platelet count.	
11. After achieving platelet engraftment, a patient does not require management in case of severe thrombocytopenia.	
12. Patients receiving Casgevy should be monitored and managed for platelet counts according to standard guidelines and medical judgement.	
KRM 2 Neutrophil Engraftment Failure	
13. For patients who have neutrophil engraftment failure a second dose of Casgevy should be considered.	15 and 16 marked as correct
14. Patients who receive CD34+ backup cells will still obtain the benefits of Casgevy.	
15. Patients who have neutrophil engraftment failure should receive CD34+ backup cells.	
16. Patients should be advised to seek medical assistance if they experience fever, chills or infections because they could be symptoms of low white blood cells.	
17. On top of monitoring and managing absolute neutrophil counts and infections according to standard guidelines and medical judgement, a regular biopsy should be performed.	
RM 3 Gene Editing-related Oncogenesis	
18. Patients should be advised to seek medical assistance if they experience any signs or symptoms of a hematologic malignancy.	18, 19, and 21 are marked as correct
19. Patients should be monitored annually, including complete blood counts, and managed according to standard guidelines and medical judgement.	
20. Patients should get a bone marrow biopsy 2 years after Casgevy treatment.	
21. If blood and/or bone marrow are collected for confirmation of a hematologic malignancy, additional samples should be taken for analysis by the marketing authorization holder to evaluate the association of malignancy with Casgevy treatment.	
RM 4 Long-term Effect	

22. Long-term effects of Casgevy are not yet known and therefore a registry-based study to follow patients who have received Casgevy is undertaken.	22, 23, and 24 are marked as correct
23. A registry-based study will be set up in which patients are followed up and treated according to standard clinical practice.	
24. Patients should be informed about the importance of enrolling in a registry-based study with 15-year follow-up.	
25. Only patients enrolled in the registry-based study for Casgevy can receive	

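### Item 17 puts neutrophil monitoring and a regular biopsy under one correct/incorrect mark, so KRM 2 cannot show whether HCPs hold the monitoring message

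*Protocol*

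**What the plan says.** Protocol section 9.7.4 fixes the items, the answer key and the success rule.

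- Scope: "Eighteen knowledge questions will test the HCPs understanding of 4 KRMs".
- Response format: "Please indicate if each provided statement is correct or incorrect".
- KRM 2 (neutrophil engraftment failure) has items 13 to 17, and its desired response is "15 and 16 marked as correct". Items 13, 14 and 17 are therefore keyed incorrect by elimination.
- Item 17: "On top of monitoring and managing absolute neutrophil counts and infections according to standard guidelines and medical judgement, a regular biopsy should be performed".
- Success rule: "The aRMM pertaining to each KRM will be considered successful if the correct rate for the specific KRM is at least 80" per cent.

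The other two engraftment and oncogenesis messages treat monitoring differently. KRM 1 has item 12, "Patients receiving Casgevy should be monitored and managed for platelet counts according to standard guidelines and medical judgement", and KRM 3 has item 19, "Patients should be monitored annually, including complete blood counts, and managed according to standard guidelines and medical judgement". Both stand alone and both are keyed correct.

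**The concern.** Item 17 is double-barrelled. It presupposes that neutrophil counts and infections are monitored and managed, and it asserts that a regular biopsy is added. A respondent has one mark for both. An HCP who marks it incorrect may be rejecting the biopsy, the monitoring, or both, and the scoring treats these alike.

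This matters because item 17 is the only place in KRM 2 where monitoring appears. The first objective (section 8) is HCPs' understanding of the Guide's safety information on each risk, neutrophil engraftment failure included. As drafted, the KRM 2 result says nothing about the monitoring part of that information, and the gap cannot be repaired after fielding: section 9.6 rules out follow-up questions.

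**Working it through.** **Coverage.** The five KRM 2 items, by content:

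| Item | Content | Key |
|---|---|---|
| 13 | Second dose | incorrect |
| 14 | Benefit after backup cells | incorrect |
| 15 | Use of backup cells | correct |
| 16 | Symptom advice to patients ("Patients should be advised to seek medical assistance if they experience fever, chills or infections") | correct |
| 17 | Monitoring (presupposed) plus regular biopsy (asserted) | incorrect |

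Item 16 is the nearest neighbour, but it concerns what patients are told about symptoms, not monitoring of counts by the HCP. The stated item total reproduces: 5 + 5 + 4 + 4 = 18.

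**Scoring of item 17.** Suppose a respondent endorses item 17 only when accepting both parts, and answers items 13 to 16 as keyed.

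| Monitoring | Biopsy | Item 17 scored | KRM 2 |
|---|---|---|---|
| accepts | rejects | right (as intended) | 5/5 |
| accepts | accepts | wrong | 4/5 |
| rejects | rejects | right | 5/5 |
| rejects | accepts | right | 5/5 |

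Rejecting monitoring never costs a mark. It gains one only for an HCP who would also have endorsed the biopsy (second row against fourth).

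**Size of the inflation.** The documents give no response rates, so these are assumptions:

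- m = share holding the monitoring message
- b = share rejecting the biopsy, independent of m
- o = correct rate on items 13 to 16, set at 80%

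The KRM 2 rate is taken as the pooled percentage of correct answers, as section 9.7.4 words it.

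- As written: [4o + 1 − m(1 − b)]/5
- Item 17 scored on the biopsy alone, still five items: (4o + b)/5
- Difference: (1 − m)(1 − b)/5

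| m | b | As written | Biopsy alone | Inflation |
|---|---|---|---|---|
| 100% | 70% | (3.2 + 0.700)/5 = 78.0% | 78.0% | 0 |
| 95% | 70% | (3.2 + 0.715)/5 = 78.3% | 78.0% | 0.3 points |
| 60% | 80% | (3.2 + 0.880)/5 = 81.6% | 80.0% | 1.6 points |
| 50% | 70% | (3.2 + 0.850)/5 = 81.0% | 78.0% | 3.0 points |

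With o = 80% and b = 70%, the score as written reaches 80% only if 1 − 0.3m ≥ 0.80, that is m ≤ 2/3. At least a third of respondents would have to lack the monitoring message.

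**What a split does.** With separate monitoring and biopsy statements, the pooled rate is (4o + m + b)/6. Two consequences follow:

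- If every HCP rejects both monitoring and biopsy and answers the rest as keyed, KRM 2 goes from 5/5 = 100% to 5/6 = 83.3%. That still passes 80%, although nobody holds the monitoring message.
- If every HCP holds the message (m = 100%, b = 70%, o = 80%), KRM 2 goes from 78.0% to (3.2 + 1.0 + 0.7)/6 = 81.7%, because an easy item has been added.

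A split therefore closes the gap only if the monitoring item is also read on its own.

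**The case against.** The strongest reply is that item 17 is not an ordinary two-claim statement. Its opening clause treats monitoring as given and only the biopsy is asserted, so it works as a distractor much like item 20, which also concerns a biopsy and is also keyed incorrect. Respondents are HCPs at centres experienced in stem cell transplantation (section 7), in a setting where the materials go to HCPs trained on Casgevy (section 9.2). Few are likely to reject neutrophil monitoring. User testing (section 9.4) precedes finalization and covers wording and clarity.

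Much of this stands, and it is why the inflation is probably small. It does not remove the gap. If monitoring is merely presupposed, it is not tested, and KRM 2 has no monitoring item under either reading. Platelet monitoring has its own item in KRM 1 although the respondents are the same. User testing as described looks at comprehension, clarity and flow, not at coverage of messages or the answer key.

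A reader might also infer that ignorance of monitoring generally raises the KRM 2 rate. It does so only among HCPs who would endorse the biopsy; for the others the score is unchanged. Nor do the figures at m = 100% show that the present wording can understate KRM 2. Item 17 then scores exactly b, and the rise from 78.0% to 81.7% comes only from the added item.

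**Conclusion.** The point holds as a coverage defect. KRM 2 cannot show whether HCPs hold the monitoring message, and an HCP who rejects monitoring is never marked down. The coverage conclusion follows from the items and the key, without any assumed rate.

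The numerical effect is secondary: 0.3 points at m = 95% and 3.0 points at m = 50%, with b = 70% and the other items at 80%. It is tempting to conclude that the wording would turn a failed KRM 2 into a success. The documents do not support that. It can be produced at m = 50%, but only by supposing that half of a transplant-experienced group lacks the message; at m = 60% and b = 80% both scorings meet 80%.

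Two assumptions remain. That neutrophil monitoring is a message of the Guide for HCPs is inferred from item 17's wording and its likeness to items 12 and 19; the Guide (Appendix 1.3) is not shown. The arithmetic uses the pooled rate of section 9.7.4, whereas the abstract words success as a share of HCPs. If that meant all items right per HCP, a split would make KRM 2 fail once more than 20% rejected monitoring. No stated figure is wrong, and nothing here judges the clinical content of the statements.

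**What to change.** Before user testing and programming:

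1. Reduce item 17 to a stand-alone statement on regular biopsy, keyed as now.
2. Add a stand-alone statement on monitoring and management of neutrophil counts and infections, worded on the pattern of item 12 and keyed according to the Guide for HCPs.
3. Update the KRM 2 desired response and change the number of knowledge questions from 18 to 19.
4. Report the correct rate of the monitoring item separately as well as within KRM 2, since the pooled rate could pass 80% while that item is answered poorly.

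The cost is one extra survey statement, an edit to the key and item count, and one extra reported line. No more respondents are needed. If the new item proves easy, it may slightly raise the pooled KRM 2 rate, which is a further reason for reporting it separately.

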#### **Data Analysis**

Data collected from the survey will be reported as descriptive statistics. Categorical variables will be summarized using counts and percentages. The main analysis will be based upon completed surveys. Subgroup analyses may be performed depending upon counts.

Percentages of correct answers will be calculated for each of the 4 Key Risk Messages (KRMs). If at least 80% of HCPs understand a KRM, that message of the aRMM will be considered successful.

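### KRM 4 items 22 and 23 put the registry study in different tenses and both are keyed correct, so wording alone can lower a score judged against 80%

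*Protocol*

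**What the plan says.** Protocol Section 9.7.4 sets four true/false statements (items 22 to 25) for KRM 4, the long-term effect. Two of them describe the state of the registry-based study:

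- Item 22: "Long-term effects of Casgevy are not yet known and therefore a registry-based study to follow patients who have received Casgevy is undertaken".
- Item 23: "A registry-based study will be set up in which patients are followed up and treated according to standard clinical practice".

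The desired response is "22, 23, and 24 are marked as correct", which leaves item 25 as the one statement to be marked incorrect.

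On scoring, the same section says "The response to each of the 18 questions will be categorized as correct or incorrect" and that "the rate of correctness (percentage of correct answers) will be summarized for each of the 4 KRMs". A KRM succeeds when its correct rate is at least 80%. The abstract (Data Analysis) words the criterion with the HCP as the unit: "If at least 80% of HCPs understand a KRM, that message of the aRMM will be considered successful".

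Section 9.6 has the knowledge questions shown one at a time in random order, with no going back and no follow-up questions. Section 9.4 plans user testing before the questionnaire is finalized. Section 6 estimates the start of data collection at Q4 2026. The Protocol does not say what stage the registry study will have reached by then.

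**The concern.** Item 22 speaks of the registry study in the present tense and item 23 in the future tense. An HCP who knows that the study is running has a reason to mark item 23 incorrect. One who knows that it is not yet running has a reason to mark item 22 incorrect. Either is scored as lacking knowledge. Because each statement appears alone and nothing further is asked, the data cannot show whether a wrong answer came from the tense or from ignorance.

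Item 22 has a second weakness. It is the only KRM 4 item that states the missing information itself, namely that long-term effects are unknown, and it ties that statement to a claim about the registry. A respondent who disputes the registry half must reject the whole item. Items 23 to 25 are about the registry only.

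At stake is a pass/fail statement on one of the four messages. With four items, each carries a quarter of the KRM 4 score.

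**Working it through.** **Inputs.** Four KRM 4 items, key 22, 23 and 24, binary scoring and the 80% threshold (Section 9.7.4); the HCP-based criterion (abstract); about 30 completed surveys (Section 9.5). The rejection rates below are assumptions shown as a range, since the Protocol gives none.

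**The plan's own figures.** The item count agrees: 5 + 5 + 4 + 4 = 18. The 80% row of Table 1 (24 of 30, 61.4% to 92.3%) reproduces with exact Clopper-Pearson limits. The plan states no figure for KRM 4 itself.

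**Step 1: one HCP.** An HCP who rejects only item 23 scores 3/4 = 75%. The tense gives an informed HCP reason to reject one of the two items, not both, so the loss from this source is at most 25 points.

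**Step 2: pooled rate, all other answers right.** With 30 HCPs there are 4 × 30 = 120 answers. If k HCPs reject item 23, the rate is (120 − k)/120.

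| HCPs rejecting item 23 | KRM 4 rate | At least 80%? |
|---|---|---|
| 6 | 95.0% | yes |
| 12 | 90.0% | yes |
| 15 | 87.5% | yes |
| 24 | 80.0% | yes |
| 25 | 79.2% | no |
| 30 | 75.0% | no |

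**Step 3: pooled rate, other items imperfect.** Let q be the proportion right on each of the other three items and p the proportion right on item 23. Then (3q + p)/4 ≥ 0.80 requires p ≥ 3.2 − 3q.

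| q | Smallest p that passes |
|---|---|
| 1.00 | 0.20 |
| 0.95 | 0.35 |
| 0.90 | 0.50 |
| 0.85 | 0.65 |

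The same formula applies to item 22 if that is the item rejected.

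**Step 4: the abstract's criterion, read as all four items right.** Success then needs at least 24 of 30 HCPs with four right answers. If item 23 is the only source of error, 6 rejections give 24/30 = 80.0% and pass; 7 give 23/30 = 76.7% and fail. If each HCP independently rejects item 23 with probability 10%, 20% or 30%, the binomial chance of at least 24 successes in 30 is 97%, 61% or 16%.

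**Step 5: weight of the missing information.** If items 23 to 25 are all answered correctly, the pooled rate reaches (3 + 0.20)/4 = 80% with item 22 right in only 20% of HCPs. KRM 4 would then pass with 24 of 30 wrong on the only item that mentions unknown long-term effects.

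**The case against.** The best defence is that the two items can both be accepted. Each refers to a registry-based study with the indefinite article. Item 22 can be taken as giving the reason for the study rather than dating it. The substance of item 23 is that follow-up and treatment follow standard practice, and that is what most respondents would judge. This stands: the items are in tension, and a reader who infers a strict contradiction goes further than the text allows, the more so because the Protocol does not give the registry's status at launch.

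A reader might also infer that KRM 4 is capped at 75%. It is not. That figure needs every respondent to reject item 23. With all else right, the pooled rate still passes when 24 of 30 do so, and nothing in the Protocol suggests a rejection rate that high.

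User testing under Section 9.4 is a real safeguard, and the wording is not final. It is described as covering comprehension, clarity and flow, however, and not as checking the key against the registry's status. It may catch the problem but is not set up to.

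On coverage, the Guide for HCPs (Appendix 1.3) is a stand-alone document and not at hand, so it cannot be shown that three registry items misrepresent its message. Nor is it right that KRM 4 leaves the missing information untested: item 22 does test it, and if nobody answered item 22 correctly the pooled rate could not exceed 75%. A low score on one item being averaged away is a property of any four-item score. What remains is narrower: the one item on the missing information carries two claims, so a wrong answer to it cannot be interpreted.

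**Conclusion.** The point holds as a wording defect in scored items. Two statements keyed correct describe the same study in different tenses, and an informed HCP who reads either literally can be scored wrong in a way the data cannot reveal.

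The size depends on which success criterion applies. On the pooled rate in Section 9.7.4 the effect is at most 25 points. It decides the result only when rejection of item 23 is common: above 80% of HCPs if the other items are perfect, above 50% if they run at 90%. On an all-four-right reading of the abstract, which the Protocol neither states nor excludes, 7 of 30 is enough.

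These figures assume 30 completed surveys and, in Step 4, no errors other than on item 23. How many HCPs would read the tense literally is unknown. The documents therefore do not show that KRM 4 will fail, only that its result can be moved by wording. The change is worth making because it is cheap and the score feeds an 80% decision.

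**What to change.** Before the questionnaire is finalized, and preferably before user testing:

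1. Make item 23 tense-neutral. Drop the clause about setting the study up and begin with *In the registry-based study, patients are…*, keeping the content on follow-up and treatment.
2. Align the verb in item 22 with the registry's actual status when the survey opens.
3. Put the missing information in its own item, for example *It is not yet known what the long-term effects of Casgevy are*, and leave the registry claim as a separate statement.
4. Update the KRM 4 key and, if an item is added, the count of 18 in Section 9.7.4 (to 19, with five items in KRM 4).

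The cost is some rewording and at most one extra question per respondent.

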## 9.7.5 Analysis for Objectives of HCPs' Awareness of the aRMM Tools

The following will be summarized using the Completed Surveys analysis set:

- The proportion who report being aware of the Guide for HCPs.
- The proportion who report having received the Guide for HCPs.
- The proportion who report having read the Guide for HCPs.
- The proportion who report being aware of the Guide for Patients/Carers.
- The proportion who have received copies of the Guide for Patients/Carers.
- The proportion who report being aware of the Patient Card.
- The proportion who have received copies of the Patient Card.

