## Rationale and Background

Casgevy received Marketing Authorization from the European Commission on 09 February 2024 for the indications of:

- The treatment of transfusion-dependent β-thalassemia (TDT) in patients 12 years of age and older for whom hematopoietic stem cell (HSC) transplantation is appropriate and a human leukocyte antigen (HLA)-matched related HSC donor is not available.
- The treatment of severe sickle cell disease (SCD) in patients 12 years of age and older with recurrent vaso-occlusive crises (VOCs) for whom HSC transplantation is appropriate and an HLA-matched related HSC donor is not available.

Delayed platelet engraftment is an important identified risk for Casgevy. Neutrophil engraftment failure and gene editing-related oncogenesis are important potential risks. As the long-term effects of Casgevy are not known, the long-term effect of Casgevy is considered to be missing information.

aRMMs, consisting of a Guide for HCPs, a Guide for Patients/Carers and a Patient Card, have been developed to inform HCPs and patients of the important identified and important potential risks and the missing information. This survey will evaluate the effectiveness of these aRMMs.

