#### 9.4 Data Sources

The data source will be surveys completed by HCPs who have counseled patients regarding Casgevy as a treatment option at ATCs.

The HCPs will receive an invitation letter to participate in the survey. The invitation letter (APPENDIX 1.2) will include: an overview of the rationale for the survey, information on how to access the survey online and a unique invitation code to ensure that the invitation is used only once. Based on survey uptake, reminder notices will be sent to those who have been invited but have not yet participated. Participating HCPs' identifying information will be collected for the purposes of providing financial compensation based on Fair Market Value, as allowed by local laws and country regulations and to comply with laws and regulations regarding notification of payments made on behalf of a pharmaceutical company.

A structured, self-administered questionnaire will be used to collect survey data (APPENDIX 1.1). It is comprised of closed-ended questions and statements with multiple response choices.

User testing will be performed prior to finalization of the questionnaire. The user testing procedure is designed to assess comprehension among HCPs regarding the words and phrases used in survey questions and response options. User testing will also assess the clarity of the survey questions as presented to the HCPs and the flow and ease of completing the survey. Findings and recommendations from the user testing will be incorporated into the survey.

The survey will be voluntary. The collection of any personal, identifying information (e.g., first name, last name, address) from respondents will only be used for processing of HCPs' financial compensation, as stated above and will be stored in a separate database.

Each individual will be randomly assigned a unique code to access the survey. Each unique code will be deactivated upon use to prevent the code from being used to complete the survey multiple times. Individuals will not have to actively "decline to complete the survey." Participants who agree to respond to the survey will begin with a screening module with questions to confirm eligibility.

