#### 9.9 Limitations of the Research Methods

Participants will be self-selected since they will voluntarily respond to the invitation to participate, so those who choose to respond to the survey may differ in their understanding of

the important safety information from those who elect not to participate. This is a common limitation of all studies that rely on voluntary participation.

It is also possible that the respondents have an acceptable understanding of the important safety information despite not using the Guide for HCPs. The survey can assess the HCPs' understanding of the important safety information but cannot clearly determine if their knowledge is a result of reading the Guide for HCPs.

All data from the survey are self-reported and therefore susceptible to possible reporting bias. An HCP may know and report the desired behavior even if they do not undertake such behavior to provide a socially desirable response.

There is also the possibility that the email invitation may be blocked or marked as spam in the HCPs' email. This can be mitigated by field staff (Medical Scientific Liaisons [MSLs]) personally discussing this study with relevant HCPs during encounters.

As TDT and SCD are rare diseases and Casgevy is a novel therapy, the number of centers treating patients with Casgevy, the number of patients eligible for Casgevy treatment, and the number of HCPs counseling eligible patients is likely to be small. To increase response rates to the survey invitation, the MSLs will emphasize the importance of the survey as part of a regulatory commitment during encounters with relevant HCPs.

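### Awareness of the three tools carries no reference time in Section 9.7.5, so recruitment contact about the survey can inflate the reported proportions

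*Protocol*

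**What the plan says.** Objective 2 (Section 8) is HCPs' awareness of the additional risk minimisation tools. Section 9.7.5 turns it into seven proportions among completed surveys.

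- Awareness, three items: "The proportion who report being aware of the Guide for HCPs", "The proportion who report being aware of the Guide for Patients/Carers" and "The proportion who report being aware of the Patient Card".
- Receipt, three items: "The proportion who report having received the Guide for HCPs", and receipt of copies for each of the two patient tools.
- Reading, one item: "The proportion who report having read the Guide for HCPs".

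None of the seven has a reference time. The two utilization outcomes in Section 9.7.6 do have one: distribution must have happened before the patient's treatment decision.

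On recruitment, Section 9.4 says the invitation letter contains "an overview of the rationale for the survey, information on how to access the survey online and a unique invitation code", and that reminders go to invitees who have not yet taken part. Section 9.5 says that face-to-face liaison contacts will be used to encourage participation. Section 9.9 counters blocked e-mails by having liaisons "personally discussing this study with relevant HCPs during encounters".

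On the rationale, the abstract says of the three tools: "This survey will evaluate the effectiveness of these aRMMs". Section 7 adds that the survey measures how far HCPs know of and use each of them by name.

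**The concern.** An HCP who had never heard of the Patient Card may learn that it exists from the letter, a reminder or a conversation about the study, and then truthfully answer that he or she is aware of it. The item as defined counts that answer the same as awareness gained when the tools were distributed at the treatment centre. Objective 2 is meant to reflect the second kind.

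The direction is upward, toward a more favourable result. The period over which it can act is not short: Section 6 plans about six months of data collection, and Sections 9.2 and 9.5 allow an extension. It cannot be repaired in the analysis, because timing that was never asked cannot be recovered.

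Section 9.9 discusses self-selection, knowledge from other sources, self-report and spam filtering; it treats liaison contact only as a remedy for poor response. The order control in Section 9.9.1 applies to the knowledge questions. Neither section mentions recruitment as a source of awareness.

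**Working it through.** **Precision at the planned size.** Table 1 in Section 9.5 gives exact two-sided 95% Clopper-Pearson intervals for 30 surveys. With x positive answers out of n, the lower limit is the 0.025 quantile of Beta(x, n − x + 1) and the upper limit is the 0.975 quantile of Beta(x + 1, n − x). All six rows reproduce to one decimal, including 61.4 to 92.3 at 80%, 73.5 to 97.9 at 90% and 88.4 to 100.0 at 100%. No stated figure is wrong. The table is labelled for correct responses, but the same limits apply to any proportion out of 30.

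**Inputs for the inflation.**

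- A: the proportion aware before any recruitment contact. Not in the documents; assumed.
- s: the share of the previously unaware who answer that they are aware because of recruitment. Not in the documents; assumed over its whole range, 0 to 1.

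**Formula.** Reported awareness = A + (1 − A)s, so inflation = (1 − A)s. It is zero when s = 0 and at most 1 − A.

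| Assumed A | s = 0 | s = 0.25 | s = 0.5 | s = 1 | Largest inflation |
|---|---|---|---|---|---|
| 60% | 60% | 70% | 80% | 100% | 40 points |
| 80% | 80% | 85% | 90% | 100% | 20 points |
| 90% | 90% | 92.5% | 95% | 100% | 10 points |

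For example, at A = 80% and s = 0.5: 0.80 + 0.20 × 0.5 = 0.90.

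**In respondents.** One prompted HCP out of 30 moves a proportion by 1/30 = 3.3 points. If 24 of 30 (80%) were aware beforehand and three of the other six were prompted, the report is 27/30 = 90%, with Table 1 limits 73.5 to 97.9; these still include 80%. If all six were prompted, it is 30/30, with limits 88.4 to 100.0; these exclude the 80% that held before recruitment. In the extreme case, then, the interval would not reveal the error.

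**Order of events.** Letter with the rationale, then any reminders and liaison contact, then the awareness items. The letter comes first by design, because it carries the access code.

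**The case against.** Five points deserve weight.

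1. *Awareness is not all of objective 2.* Four of the seven items in Section 9.7.5 concern receipt or reading, and Section 9.7.6 adds distribution to patients. A letter that mentions a tool does not deliver it, so high awareness with low receipt would still expose poor distribution. This stands. A reader might infer that objective 2 cannot detect a failed local distribution plan; the section itself contradicts that. The protection is partial, however: the receipt and reading items are undated too, a prompted HCP could obtain or open a guide before logging in, and no reading item is listed for the two patient tools.

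2. *The documents do not say that the letter or the liaisons name the tools.* This also stands. Section 9.4 promises only an overview of the rationale, and Section 9.9 has liaisons stress the survey's importance as a regulatory commitment. A reader might infer that recruitment creates the awareness that is reported. The text supports only that it can: the stated rationale concerns these tools, so a letter that gives the rationale may well mention them.

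3. *The item wording is not shown.* Section 9.7.5 lists analyses. The questionnaire (Appendix 1.1) may already carry an anchor, and user testing is still to come. This is a reason to check, and to put the definition into Section 9.7.5 as well.

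4. *Prior awareness may be high.* Eligible HCPs have counselled at least one patient about Casgevy (Section 9.2.1), trained HCPs at treatment centres are given the tools (Section 9.2), and they must hand the patient tools over (Section 7). If so, 1 − A is small. But whether that distribution worked is what objective 2 is meant to show, so it cannot be taken as given.

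5. *No decision rests on awareness.* Correct: the 80% criterion in Section 9.7.4 applies to the key risk messages alone. Awareness is nevertheless one of three stated objectives.

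**Conclusion.** The point holds as a possible and avoidable upward bias. The three awareness proportions can be inflated by recruitment, the receipt and reading proportions less so, and the protocol neither dates the items nor lists this limitation.

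The size cannot be fixed from the documents. It lies between 0 and 1 − A: 0 to 20 points at an assumed prior awareness of 80%, and 0 to 10 at 90%. A reader might infer a guaranteed minimum, or that the figure must approach 100%. Neither follows, because a prompted share of zero or close to it is not excluded.

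The knowledge scores and the 80% criterion are not affected by how the awareness items are dated. The conclusion assumes that the questionnaire in Appendix 1.1 has no anchor of its own; if it has one, what remains is to bring Section 9.7.5 into line with it.

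**What to change.** Check Appendices 1.1 and 1.2 for an existing time anchor and for how the letter describes the tools. Then:

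- In Section 9.7.5 and the matching questionnaire items, define the outcomes as aware of, received, or read *before being invited to this survey*.
- Offer three answers: *yes, before the invitation*; *only since the invitation*; *no*. Count only the first in the main proportion and report the second separately, which shows directly how much recruitment added.
- Present awareness alongside receipt and, for the HCP Guide, reading.
- Add awareness prompted by recruitment to the limitations in Section 9.9.

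Barring the letter or the liaisons from naming the tools would go further, but it would restrict materials that are not shown and is debatable; the anchored items do not need it.

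The cost is a clause and one extra answer option per item, made before user testing. Respondents will make some recall errors about timing, and the awareness figure may come out less favourable.
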